4.3 Study Stopping Rules

Once at least 15 patients have been treated with idelalisib, study enrollment will be paused for safety evaluation if any of the following occur:

1. The number of patients with reported Grade 5 toxicity in the loncastuximab tesirine arm is more than twice the number of patients with reported Grade 5 toxicity in the idelalisib arm.
2. Grade 4 skin toxicity is reported in >2 patients treated with loncastuximab tesirine and the incidence of Grade 4 skin toxicity in patients treated with loncastuximab tesirine is >5% and the incidence is at least 50% higher than the incidence in patients treated with idelalisib.
3. Grade 4 toxicity of edema or effusion is reported in >2 patients treated with loncastuximab tesirine and the incidence of Grade 4 toxicity of edema or effusion in patients treated with loncastuximab tesirine is >5% and at least 50% higher than the incidence in patients treated with idelalisib.

Safety evaluation will be performed by ADCT.

5 Patient Population

Patients must meet all inclusion criteria and none of the exclusion criteria to be eligible for the study. All criteria have to be assessed during Screening, unless otherwise specified.

Prospective approval of protocol deviations to recruitment and enrollment criteria, also known as protocol waivers or exemptions, is not permitted.

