Grade 4 infusion related reaction	
• Permanently discontinue loncastuximab tesirine
Hy's law (AST and/or ALT $> 3 \times \text{ULN}$ and bilirubin $> 2 \times \text{ULN}$)	
• Permanently discontinue loncastuximab tesirine. Hy's law defined as: AST and/or ALT $> 3 \times \text{ULN}$ and bilirubin $> 2 \times \text{ULN}$, and without initial findings of cholestasis (ALP activity $< 2 \times \text{ULN}$) and no other reason that could explain the combination of increased transaminases and serum total bilirubin, such as viral hepatitis A, B, or C, preexisting or acute liver disease, or another drug capable of causing the observed injury

Table 5. Criteria for Dose Delay or Dose Modification of Idelalisib

Toxicity	Idelalisib
Grade ≥ 2 symptomatic pneumonitis of any severity	Permanently discontinue idelalisib
Grade 2 increased ALT/AST/bilirubin or diarrhea	Maintain idelalisib dose. Monitor at least weekly until normal
Grade 3 increased ALT/AST/bilirubin or diarrhea	Withhold idelalisib. Monitor at least weekly until normal, then may resume idelalisib at 100 mg BID.
Grade 4 increased ALT/AST/bilirubin or diarrhea	Discontinue idelalisib permanently
Grade 3 neutropenia and/or thrombocytopenia	Maintain Idelalisib dose. Monitor ANC and/or platelet count at least weekly
Grade 4 neutropenia and/or thrombocytopenia	Withhold idelalisib. Monitor ANC and/or platelet count at least weekly. When neutropenia and thrombocytopenia are Grade 3 or less, may resume idelalisib at 100 mg BID
Grade ≥ 3 sepsis or pneumonia	Withhold idelalisib until infection has resolved.
Active CMV infection of any grade or viremia (positive PCR or antigen test)	Withhold idelalisib until the infection and viremia have resolved. If idelalisib is resumed, monitor by PCR or antigen for CMV reactivation at least monthly.
Suspected PJP infection of any grade.	Withhold idelalisib. Permanently discontinue idelalisib if PJP infection is confirmed.
Other Grade ≥ 3 non-hematologic toxicities	Withhold idelalisib until resolved, then may resume idelalisib at 100 mg BID. If the same grade ≥ 3 toxicity recurs after resuming idelalisib, permanently discontinue idelalisib
Anaphylaxis, Intestinal Perforation, Stevens-Johnson syndrome (SJS) and toxic epidermal necrolysis (TEN)	Permanently discontinue idelalisib

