8.2 Eliciting and Reporting Adverse Events/Serious Adverse Events

Patients will be instructed to contact the Investigator at any time after ICF signature if any symptoms develop. At each study visit, patients will be asked a nonleading question to elicit any medically related changes in their well-being. Patients may also report AEs voluntarily and they will be instructed to contact the Investigator between visits if any symptoms develop or worsen.

AEs will be reported starting when the patient provides written informed consent. Clinically significant medical conditions present at the time of ICF signature will be reported as medical history. Clinically significant medical conditions that start or worsen after ICF signature will be reported as AEs.

All AEs, regardless of relationship to study treatment, will be reported from the time the patient signs the ICF until 30 days after the last dose of study treatment.

All SAEs, regardless of relationship to study treatment, will be reported from the date patient signs the ICF until at least 76 days after last dose of study drug, or start of new anticancer therapy, whichever is earlier; thereafter, only related SAEs will be reported.

Whenever possible, AEs should be reported as a diagnosis rather than individual signs and symptoms. If no diagnosis is available or has been identified, then the primary symptom is reported.

In general, the term ‘disease progression’ should not be used for reporting an AE/SAE. However, AEs/SAEs that are complications of disease progression should be reported.

All AEs reported or observed during the study will be recorded on the AE page of the eCRF. Information to be collected will include event term, date of onset, assessment of severity (Section 8.3), seriousness (Section 8.1), relationship to study treatment (Section 8.4), action taken with study treatment, date of resolution of the event or ongoing (when no resolution by the end of the reporting period), any required treatment or evaluations, and outcome.

New SAEs and any recurrent episodes, progression, or complications of the original SAE must be reported to the pharmacovigilance department of the Sponsor or delegate (e.g., contract

research organization [CRO]) within 24 hours after the time site personnel first learn about the event. Reporting will occur through the EDC system.

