8.3 Assessment of Severity

The AEs will be graded according to CTCAE v5.0. For events not included in the CTCAE criteria, the severity of the AE is graded on a scale of 1 to 5 as shown in [Table 7](#).

Table 7. Definition of Severity Grades for CTCAE

Grade	Definition
1	Mild; asymptomatic or mild symptoms; clinical or diagnostic observations only; intervention not indicated.
2	Moderate; minimal, local or noninvasive intervention indicated; limiting age-appropriate instrumental activities of daily living (ADL). ^a
3	Severe or medically significant but not immediately life threatening; hospitalization or prolongation of hospitalization indicated; disabling; limiting self-care ADL. ^b
4	Life-threatening consequences; urgent intervention indicated.
5	Death related to adverse event.

^a ADL refers to preparing meals, shopping for groceries or clothes, using the telephone, managing money, etc.

^b Self-care ADL refers to bathing, dressing and undressing, feeding self, using the toilet, taking medications, and not bedridden.

The AEs characterized as intermittent do not require documentation of onset and duration of each episode.

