9.8.1 Adverse Events

The focus of AE summarization will be on TEAEs. A TEAE is defined as an AE that occurs or worsens in the period extending from the first dose of study treatment until 30 days after the last dose of study treatment or start of new anti-cancer therapy, whichever is earlier.

All TEAEs will be summarized. Summary tables will be presented to show the number of patients reporting TEAEs by severity grade and corresponding percentages. A patient who reports multiple TEAEs within the same Preferred Term (or System Organ Class) is counted only once for that Preferred Term (or System Organ Class) using the worst severity grade.

Separate summaries will be prepared for TEAEs classified as severe or life-threatening (\geq Grade 3); study treatment-related AEs; AEs leading to treatment interruption, modification, or discontinuation; SAEs; and death.

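### Read literally, stopping rules 2 and 3 leave out fatal skin or edema/effusion cases, so some mixed clusters trigger no pause once idelalisib has a Grade 5 event

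*Combined protocol and SAP*

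**What the plan says.** Protocol Section 4.3 opens: "Once at least 15 patients have been treated with idelalisib, study enrollment will be paused for safety evaluation if any of the following occur". Three rules follow.

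- Rule 1 compares patients with Grade 5 toxicity of any kind: it is met when the loncastuximab tesirine count "is more than twice the number of patients with reported Grade 5 toxicity in the idelalisib arm".
- Rule 2 requires that "Grade 4 skin toxicity is reported in >2 patients treated with loncastuximab tesirine", that the incidence of Grade 4 skin toxicity in that arm exceeds 5%, and that this incidence is at least 1.5 times the idelalisib incidence.
- Rule 3 has the same structure: "Grade 4 toxicity of edema or effusion is reported in >2 patients treated with loncastuximab tesirine", with the same 5% and 1.5-fold conditions.

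In rules 2 and 3 both the patient count and the incidence refer to Grade 4 alone. Table 7 in Section 8.3 keeps life-threatening events (Grade 4) apart from Grade 5, defined as "Death related to adverse event". Where the protocol means a grade or worse, as in Table 4, it uses the ≥ sign. Section 4.3 does not say how to count a patient first reported at Grade 4 who then dies. Section 9.8.1 has a convention under which a patient "is counted only once for that Preferred Term (or System Organ Class) using the worst severity grade", but it governs the treatment-emergent adverse event tables, not the stopping rules.

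**The concern.** A rule meant to detect a cluster of a named severe toxicity should not become harder to meet because some of the cases were fatal. Read literally, each death moves a patient out of rule 2 or 3 and into rule 1, and rule 1 depends on idelalisib deaths that may have nothing to do with skin or fluid toxicity. Whether a mixed cluster pauses enrollment can then turn on an unrelated death in the comparator arm. What is at stake is the pre-specified trigger, not whether the sponsor knows of the deaths.

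**Working it through.** **Inputs.** The rules are those of Section 4.3 and the grades those of Table 7. Allocation is 2:1 (Section 4.1). I assume that treated patients follow the same ratio, so the rules start at about 30 v 15. The documents state no operating characteristics for these rules, so there is no figure of the plan's to reproduce.

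**Step 1: apply the rules as written.** Let L4 and L5 be the loncastuximab tesirine patients with Grade 4 and fatal cases of one named toxicity, with no other death in that arm, and I5 the idelalisib Grade 5 count. Rule 1 is met if L5 > 2 × I5. Rule 2 is met if L4 > 2, L4/nL > 5%, and L4/nL is at least 1.5 times the idelalisib rate.

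With I5 = 0, a single loncastuximab tesirine death meets rule 1 (1 > 0), so there is no gap. With I5 = 1, rule 1 needs L5 > 2, that is, three deaths. With none of the toxicity at Grade 4 on idelalisib:

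| L4 | L5 | Rule 1 (L5 > 2) | Rule 2 (L4 > 2) | Pause as written | Grade 4-5 rate, 30 v 15 | Grade 4-5 rate, 40 v 20 |
|---|---|---|---|---|---|---|
| 3 | 0 | no | yes | **yes** | 3/30 = 10.0% | 3/40 = 7.5% |
| 2 | 1 | no | no | **no** | 10.0% | 7.5% |
| 1 | 2 | no | no | **no** | 10.0% | 7.5% |
| 2 | 2 | no | no | **no** | 4/30 = 13.3% | 4/40 = 10.0% |

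Rule 3 behaves in the same way. With I5 = 2 the gap widens: at 30 v 15, four fatal cases and no Grade 4 case meet no rule (4 > 4 is false).

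**Step 2: how long the gap lasts.** The 5% condition bounds it. Three cases exceed 5% up to 59 loncastuximab tesirine patients (3/59 = 5.1%; 3/60 = 5.0%, not above). Four cases exceed it up to 79 (4/79 = 5.1%; 4/80 = 5.0%). Beyond that, larger clusters are needed. At 100 v 50 with I5 = 1, five Grade 4 cases plus one fatal case (6%) is still missed.

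**Step 3: how often it matters.** I simulated enrollment in blocks of two loncastuximab tesirine and one idelalisib patient. The rules were checked after each block from 15 to 49, events were counted at entry, and one named toxicity was modelled. A loncastuximab tesirine death that precedes any idelalisib death once the rules are active therefore pauses the trial, as it should. The event rates are assumptions: 10-50% of Grade 4-5 cases fatal, and 2-4% background Grade 5 in both arms. A missed pause is a trial with no pause as written that would pause if Grade 4-5 events were also tested against the same three conditions.

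| True Grade 4-5 rate (loncastuximab tesirine / idelalisib) | Missed pauses, every fatal case lost | Missed pauses, half of fatal cases still counted as Grade 4 |
|---|---|---|
| 8% / 0% | 0.6-2.9% | 0.3-1.2% |
| 8% / 3% | 0.7-4.2% | 0.4-1.8% |
| 4% / 0% | 1.3-3.9% | not run |
| 6% / 0% | 1.1-4.2% | not run |
| 10% / 0% | 0.3-1.4% | not run |

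At 8% / 0% with every fatal case lost, some pause occurs in 96-98% of trials as written and in 98-99% with the extra test.

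**Step 4: test the obvious rewording.** Replacing Grade 4 by Grade 4 or higher also lets a fatal idelalisib case raise the comparator rate. Take 31 v 15, three Grade 4 skin cases on loncastuximab tesirine and one fatal skin case on idelalisib. As written, 3/31 = 9.7% against 0%: pause. After replacement, the idelalisib rate is 1/15 = 6.7%, the bar is 1.5 × 6.7% = 10.0%, and 9.7% falls short: no pause. Table 5 lists Stevens-Johnson syndrome and toxic epidermal necrolysis among the reasons to stop idelalisib permanently, so such a case can arise. In the 8% / 3% runs, replacement would lose a pause in 0.5-0.9% of trials. An added trigger loses none.

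**The case against.** The strongest reply is that the gap depends on one reading. The rules ask in how many patients Grade 4 toxicity is reported, and a patient reported at Grade 4 who later dies can still be said to meet that. Section 8.2 makes a prior Grade 4 report plausible: "New SAEs and any recurrent episodes, progression, or complications of the original SAE must be reported to the pharmacovigilance department of the Sponsor", within 24 hours. If every fatal case had first been reported at Grade 4 and still counted, the gap would vanish. This stands as a limit on size, but Section 4.3 does not settle the reading, and some fatal cases may never be reported at Grade 4.

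It can also be said that giving deaths to rule 1 and non-fatal events to rules 2 and 3 is a coherent division. It is, until an idelalisib death raises the bar in rule 1. From then on the division makes a cluster harder to act on when some of its cases are fatal.

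The assumed rates have no support in the documents. The common Grade 3 or worse Phase 1 events listed in Section 1.2.3, down to 5.5%, include no skin, edema or effusion term, although that list covers all B-cell lymphoma patients in a dose-escalation study and counts terms separately. Several fatal cases of one such toxicity together with an idelalisib death would be unusual. This stands, and is why the point is minor.

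The added trigger also raises false pauses about as much as true ones: by up to 3.3 percentage points when both arms share the same 1-3% rate, against up to 2.9% of trials gained at 8% / 0%. This stands too.

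Simple replacement would still be a net gain in the 8% / 3% runs, from 0.73 − 0.59 = 0.14 to 4.22 − 0.62 = 3.60 points, and at exactly 30 v 15 three cases against one gives exactly 1.5-fold and still pauses. That is fair, but an added sentence gives the same gain without the loss.

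Finally, the sponsor hears of every fatal serious event within 24 hours and can stop the study at any time, and a pause only leads to the sponsor's own evaluation. That limits the harm. It does not replace a stated trigger.

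**Conclusion.** The concern holds as a minor point. On a literal reading of Section 4.3, and once idelalisib has at least one Grade 5 event of any cause, certain mixtures of Grade 4 and fatal cases of a named toxicity meet no rule, although fewer non-fatal cases would. The enumeration rests only on the protocol's wording and 2:1 treated numbers. The frequency rests on assumed rates: about 0.3-4.2% of trials across the scenarios examined with a true rate of 4-10%, and toward the lower end if many fatal cases were reported at Grade 4 first and still count. With no idelalisib Grade 5 event there is no gap.

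**What to change.** Keep rules 2 and 3 as they are and add to each: *Enrollment is also paused if the same three conditions are met when Grade 4 or higher events are counted in both arms, each patient once.* Do not substitute Grade 4 or higher for Grade 4, for the reason in Step 4. Leave rule 1, the thresholds and the sponsor's evaluation unchanged. Two fatal cases alone against one idelalisib death would still not pause enrollment, in line with the existing requirement of more than two patients.

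The cost is one sentence in each of two rules, with no new data, staff or procedures, and a slightly higher chance of a pause. At true rates of 1-3%, with the same fatality and background assumptions, the chance of any pause rises by 0.1-2.8 percentage points if idelalisib has none of the toxicity and by 0.1-3.3 points if it has the same rate. As written, that chance is already 64-82%. A pause is reversible.

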5.1 Inclusion Criteria

1. Written informed consent must be obtained prior to any study procedures.
2. Male or female patients aged 18 years or older, with pathologic diagnosis of FL (Grade 1, 2, 3A) in the most recent tumor biopsy.
3. Relapsed or refractory disease following two or more treatment regimens, at least one of which must have contained an anti-CD20 therapy.
4. Patients who have received previous CD19-directed therapy must have a biopsy which shows CD19 expression after completion of the CD19-directed therapy.
5. Measurable disease as defined by the 2014 Lugano Classification as assessed by PET-CT or, if not FDG avid, CT or magnetic resonance imaging (MRI).
6. Availability of formalin-fixed paraffin-embedded (FFPE) tumor tissue block (or minimum 10 freshly cut unstained slides if block is not available).

Note: Any biopsy since initial diagnosis is acceptable, but if several samples are available, the most recent sample is preferred.

7. Eastern Cooperative Oncology Group (ECOG) performance status 0 to 2.
8. Adequate organ function as defined by screening laboratory values within the following parameters:
 - a. Absolute neutrophil count (ANC) $\geq 1.0 \times 10^3/\mu\text{L}$ (off growth factors at least 72 hours),
 - b. Platelet count $\geq 75 \times 10^3/\mu\text{L}$ without transfusion in the past 2 weeks,
 - c. Alanine aminotransferase, AST, and GGT $\leq 2.5 \times$ the upper limit of normal (ULN),
 - d. Total bilirubin $\leq 1.5 \times$ ULN (patients with known Gilbert's syndrome may have a total bilirubin up to $\leq 3 \times$ ULN).
 - e. Calculated creatinine clearance $\geq 30 \text{ mL/min}$ by the Cockcroft and Gault equation.

Note: A laboratory assessment may be repeated a maximum of two times during the Screening period to confirm eligibility

9. Women of childbearing potential (WOCBP)* must agree to use a highly effective method** of contraception from the time of giving informed consent until at least 9 months after the last dose of study treatment. Men with female partners who are of childbearing potential must agree to use a condom when sexually active or practice total abstinence from the time of giving informed consent until at least 6 months after the patient receives his last dose of study treatment.

* Women of childbearing potential are defined as sexually mature women who have not undergone bilateral tubal ligation, bilateral oophorectomy, or hysterectomy; or who have not been postmenopausal. A postmenopausal state is defined as no menses for 12 months without an alternative medical cause. A high follicle stimulating hormone (FSH) level in the postmenopausal range may be used to confirm a postmenopausal state in women not using hormonal contraception or hormonal replacement therapy. However, in the absence of 12 months of amenorrhea, a single FSH measurement is insufficient.

** Highly effective forms of birth control are methods that achieve a failure rate of less than 1% per year when used consistently and correctly. Highly effective forms of birth control include hormonal contraceptives associated with inhibition of ovulation (oral, injectable, patch, intrauterine devices), male partner sterilization, or total abstinence from heterosexual intercourse, when this is the preferred and usual lifestyle of the patient.

Note: The double-barrier method (e.g., synthetic condoms, diaphragm, or cervical cap with spermicidal foam, cream, or gel), periodic abstinence (such as calendar, symptothermal, post ovulation), withdrawal (coitus interruptus), lactational amenorrhea method, and spermicide-only are not acceptable as highly effective methods of contraception.

5.2 Exclusion Criteria

1. Previous treatment with loncastuximab tesirine.
2. Previous treatment with idelalisib.
3. History of hypersensitivity to any of the excipients of loncastuximab tesirine or idelalisib.
4. Follicular lymphoma which has transformed to DLBCL or other aggressive lymphomas.
5. Requires treatment or prophylaxis with a strong cytochrome P450 (CYP) 3A inhibitor, inducer, or sensitive substrate.
6. History of or ongoing drug-induced pneumonitis.
7. History of or ongoing inflammatory bowel disease.
8. Any condition that could interfere with the absorption or metabolism of idelalisib including malabsorption syndrome, disease significantly affecting gastrointestinal function, or resection of the stomach or small bowel.

9. Active second primary malignancy other than non-melanoma skin cancers, non-metastatic prostate cancer, in situ cervical cancer, ductal or lobular carcinoma in situ of the breast, or other malignancy that the Sponsor's medical monitor and Investigator agree and document should not be exclusionary.
10. Autologous transplant within 30 days prior to start of study treatment (C1D1).
11. Allogenic transplant within 60 days prior to start of study treatment (C1D1).
12. Active graft-versus-host disease.
13. Post-transplantation lymphoproliferative disorders.
14. Human immunodeficiency virus (HIV) seropositive with any of the following:
 - a. CD4+ T-cell counts <350 cells/ μ L.
 - b. Acquired immuno-deficiency syndrome (AIDS)-defining opportunistic infection within 12 months prior to screening.
 - c. Not on anti-retroviral therapy, or on anti-retroviral therapy for < 4 weeks at the time of screening.
 - d. HIV viral load \geq 400 copies/mL.
15. Serologic evidence of chronic hepatitis B infection and unable or unwilling to receive standard prophylactic anti-viral therapy or with detectable hepatitis B virus (HBV) viral load.
16. Serologic evidence of hepatitis C infection without completion of curative treatment or with detectable hepatitis C virus (HCV) viral load.
17. History of Stevens-Johnson syndrome or toxic epidermal necrolysis.
18. Lymphoma with active central nervous system involvement, including leptomeningeal disease.
19. Clinically significant third space fluid accumulation (i.e., ascites requiring drainage or pleural effusion that is either requiring drainage or associated with shortness of breath).
20. Breastfeeding or pregnant.
21. Significant medical comorbidities, including but not limited to, uncontrolled hypertension (BP \geq 160/100 mm Hg repeatedly), unstable angina, congestive heart failure (greater than New York Heart Association class II), electrocardiographic evidence of acute ischemia, coronary angioplasty or myocardial infarction within 6 months prior to screening, uncontrolled atrial or ventricular cardiac arrhythmia, poorly controlled diabetes, or severe chronic pulmonary disease.
22. Any Grade \geq 3 active infection which requires IV antibiotics, IV antiviral, or IV antifungal treatment.
23. Major surgery, radiotherapy, chemotherapy or other anti-neoplastic therapy within 14 days prior to start of study treatment (C1D1), except shorter if approved by the Sponsor.

24. Use of any other experimental medication within 30 days prior to start of study treatment (C1D1).
25. Live vaccine administration within 4 weeks prior to Cycle(C) 1 Day (D) 1.
26. Failure to recover to \leq Grade 1 (Common Terminology Criteria for Adverse Events [CTCAE] version 5.0) from acute non-hematologic toxicity (except \leq Grade 2 neuropathy or alopecia) due to previous therapy prior to screening.
27. Any other significant medical illness, abnormality, or condition that would, in the Investigator's judgment, make the patient inappropriate for study participation or put the patient at risk.

